5.2.2 Inclusion Criteria

1. Newly diagnosed GBM with histopathological confirmation.

2. Surgically suitable for subtotal or gross total resection as determined by central review.

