4 HYPOTHESIS AND SPECIFIC AIMS

4.1 Hypothesis

After standard treatment of GBM with resection and adjuvant therapy, local failure is the dominant pattern of failure. Neoadjuvant therapy consistently provides the potential for improved local control and removal of residual stem cell niches. The hypothesis is that earlier institution of neoadjuvant chemoradiation therapy in GBM would improve local control and potentially overall survival.

Involved field radiation is often employed to treat unresectable or sub totally resected GBM. Radiating native GBM is not uncommon as many tumors are not safely resectable due to its location in eloquent brain. Also, surgical resection is often performed in patients who recur

after initial definitive treatment with chemo radiation. Hence, this approach of chemoradiation of native glioblastomas and surgical resection after prior chemoradiation is not entirely new. However, planned neoadjuvant chemoradiation prior to immediate surgical resection in glioblastoma is a novel approach.

4.2 Specific Aim 1

Feasibility of neoadjuvant therapy in GBM to improve local control (local progression free survival) without significant impact of preoperative chemotherapy and radiation on surgical resection.

4.3 Specific Aim 2

To determine the progression free survival with this approach.

Assess the impact of improvements in local control on overall survival.

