5.2.3 Exclusion Criteria

1. Recurrent, unresectable or multifocal malignant gliomas.
2. Any site of distant disease (for example, drop metastases from the GBM tumor site)
3. Prior radiation or chemotherapy or radiosensitizers for cancers of the brain and head and neck region; note that prior chemotherapy for a different cancer is allowable (except temozolomide).
4. Pregnancy or women of childbearing potential and men who are sexually active and not willing/able to use medically acceptable forms of contraception; this exclusion is necessary because the treatment involved in this study may be significantly teratogenic.
5. Patients treated on any other therapeutic clinical protocols within 30 days prior to registration.
6. Inability to undergo MRI (e.g., due to safety reasons, such as presence of a pacemaker, or severe claustrophobia).
7. Severe, active co-morbidity, defined as follows:
 - a. Transmural myocardial infarction within the last 6 months prior to registration
 - b. History of recent myocardial infarction 1month prior
 - c. New York Heart Association grade II or greater congestive heart failure requiring hospitalization within 3 months prior to registration.

- d. Serious or non-healing wound, ulcer or bone fracture or history of abdominal fistula, intra-abdominal abscess requiring major surgical procedure, open biopsy or significant traumatic injury within 28 days prior to registration, with the exception of the craniotomy for surgical resection
- e. Acute bacterial or fungal infection requiring intravenous antibiotics at the time of registration
- f. Hepatic insufficiency resulting in clinical jaundice and/or coagulation defects; note, however, that laboratory tests for coagulation parameters are not required for entry into this protocol.
- g. Chronic obstructive pulmonary disease exacerbation or other respiratory illness requiring hospitalization or precluding study therapy at the time of registration
- h. Acquired immune deficiency syndrome (AIDS) based upon current CDC definition; note, however, that HIV testing is not required for entry into this protocol. The need to exclude patients with AIDS from this protocol is because the treatments involved in this protocol may be significantly immunosuppressive with potentially fatal outcomes in patients already immunosuppressed.
- i. Any other severe immunocompromised condition.

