CTV_6000 - Contrast-enhancing T1 abnormality plus a margin of 1-2 cm. The CTV_6000 margin may be reduced around natural barriers to tumor growth such as the skull, ventricles, falx, etc.

PTV_4600, PTV_5100- In general the PTV is the CTV plus a geometric 4 mm expansion in all dimensions. PTV may extend beyond bony margins and the skin surface.

Dose Prescription:

>95% of the volume to receive at least 4600cGy (PTV_4600), 5100cGy (PTV_5100) or 6000cGy (PTV_6000) respectively. D95 of up to 95% will be allowed to meet OAR (Organs at risk dose constraints. D95 of 95-90% would a be minor violation. D95<90% is not allowed.

Treatment Planning Priorities

1. Spinal Cord
2. Brain Stem core
3. Brain Stem surface
4. Optic Chiasm PRV
5. Optic Nerve L PRV and Optic Nerve R PRV

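### No criterion excludes prior resection of the current tumor, and exclusion 7d exempts a pre-registration resection craniotomy, which conflicts with the biopsy, chemoradiation, then surgery design

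*Combined protocol and SAP*

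**What the plan says.** Exclusion 7d (5.2.3), listed under severe co-morbidity, covers serious wounds and certain recent procedures. It ends: "open biopsy or significant traumatic injury within 28 days prior to registration, with the exception of the craniotomy for surgical resection".

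The other criteria that bear on earlier surgery are these:

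- Inclusion 1 (5.2.2): "Newly diagnosed GBM with histopathological confirmation". It names no tissue source.
- Inclusion 2 (5.2.2): "Surgically suitable for subtotal or gross total resection as determined by central review". It asks whether a resection can be done, not whether one has been done.
- Exclusion 1 (5.2.3): "Recurrent, unresectable or multifocal malignant gliomas". Prior resection is not listed.
- Exclusion 3 (5.2.3): "Prior radiation or chemotherapy or radiosensitizers for cancers of the brain and head and neck region". Surgery is not mentioned.

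The rest of the plan describes a tumor left in place until after chemoradiation. Section 4.1 states that "planned neoadjuvant chemoradiation prior to immediate surgical resection in glioblastoma is a novel approach". Section 5.5 defines the experimental element as choosing resectable patients and giving chemoradiation before surgery. Section 5.5.3 has the diagnosis made by stereotactic or open biopsy, with stereotactic preferred. The 5.6 table puts biopsy at screening, chemoradiation in weeks 1-7 and surgery in weeks 8-12. The boost volume in 5.5.4 is "CTV_6000 - Contrast-enhancing T1 abnormality plus a margin of 1-2 cm", and no target definition mentions a resection cavity.

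**The concern.** The feature that makes this trial new is that the tumor is unresected when chemoradiation starts. The eligibility criteria do not require that, and one of them exempts an event that would contradict it. Protocol surgery comes after registration, so the 7d exemption has nothing to act on at registration unless a resection has already taken place.

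Both stages are affected if such patients enter. Stage 1 (5.7) counts progression precluding surgery and major surgical complications. In an already-resected patient the protocol operation is a reoperation, which says little about the safety of a first resection after chemoradiation. The efficacy decision (5.9.2) counts patients without progression at 7 months, and section 3.1 itself reports that extent of resection is associated with survival. A group mixing one-resection and two-resection patients does not cleanly answer whether chemoradiation before first resection works.

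**Working it through.** **Step 1. Apply the criteria to one patient.** Take newly diagnosed glioblastoma, partial resection three weeks before registration, and residual tumor judged resectable.

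| Criterion | Result for this patient |
|---|---|
| Inclusion 1 | Met on its wording; contestable if 5.5.3 is read into it |
| Inclusion 2 | Met: the residual tumor is suitable for resection |
| Exclusion 1 | Does not apply: not recurrent, unresectable or multifocal |
| Exclusion 3 | Does not apply: no prior radiation or drug treatment |
| Exclusion 7d | Does not apply: the resection craniotomy is exempted |

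Nothing in 5.2 stops registration on this point. Section 5.5.7 disallows debulking surgery as supportive therapy on study, but that is not an entry criterion. The same section bars carmustine wafers, tumor treating fields and brachytherapy before study entry. Prior resection is not in that list.

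**Step 2. Compare the treatment course.** Intended: biopsy, chemoradiation, resection. This patient: resection, chemoradiation, re-resection.

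**Step 3. Reproduce the decision rule.** Inputs from 5.9.2: n1 = 11, stop if 6 or fewer are progression-free, n = 25, reject at 17 or more, p0 = 0.50, p1 = 0.75. The probability of passing at a true rate p is

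P(pass) = Σ (x = 7 to 11) P[Bin(11, p) = x] × P[Bin(14, p) ≥ 17 − x].

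- At p = 0.50: 0.0458, within the stated 0.05.
- At p = 0.75: 0.8005, matching the stated 80%.

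The design figures are sound; the point is about who enters, not about the arithmetic.

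**Step 4. Size.** Each patient is 1/25 = 4% of the decision set. The documents give no number k of already-resected patients and no 7-month rate q for them. Both are assumptions below. The average rate is p = b(1 − k/25) + q(k/25), where b is the rate in the intended population, and p goes into the formula above as a common rate for all patients.

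| k | b = 0.75, q = 0.50 (power) | b = 0.75, q = 0.60 (power) | b = 0.50, q = 0.60 (false pass) | b = 0.50, q = 0.75 (false pass) |
|---|---|---|---|---|
| 0 | 80.05% | 80.05% | 4.6% | 4.6% |
| 1 | 76.8% | 78.2% | 5.0% | 5.6% |
| 2 | 73.4% | 76.2% | 5.4% | 6.8% |
| 5 | 62.0% | 69.8% | 6.8% | 11.5% |
| 10 | 41.7% | 58.0% | 9.8% | 24.0% |

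Example: k = 2, b = 0.75, q = 0.50 gives p = 0.75 × 0.92 + 0.50 × 0.08 = 0.73 and P(pass) = 0.734.

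The first two columns show a loss of power if these patients do worse than the intended population; the last two show a raised false-pass rate if they do better. The table shows sensitivity only, because nothing in the documents picks a column or a row.

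**The case against.** The strongest reply is that the intended population is clear. Section 5.5.3 calls histological confirmation an eligibility requirement and says that it is obtained by biopsy. The 5.6 table shows one resection, after chemoradiation. Sections 4.1 and 5.5 define the sequence, and central review looks at every patient's surgical suitability. Exclusion 7d sits in a co-morbidity list: its exception only stops a craniotomy from counting as a recent wound or procedure, makes nobody eligible by itself, and may be stray wording.

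Much of this stands. The documents do not show that the sponsor meant to admit resected patients or that any would enroll. But 5.5.3 describes a procedure and does not say that other tissue sources disqualify. Central review is asked about suitability for resection, not about earlier surgery. And 7d is a written rule that conflicts with the sequence, which is more than silence.

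Two stronger readings are tempting. A reader might infer that patients given ordinary postoperative chemoradiation can be counted. The documents do not support that: a registered patient must still be a resection candidate, unresectable tumors are excluded, and protocol surgery is scheduled. A reader might also infer that one or two such patients would lift 15 or 16 successes to 17. That is true of any one or two successes in 25; it assumes that the patients whose places they took would have progressed, and the documents give neither frequency nor direction.

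**Conclusion.** The point holds as an eligibility conflict. No criterion excludes prior resection of the current tumor, and exclusion 7d exempts a resection craniotomy before registration, contrary to the biopsy, chemoradiation, then surgery design. The conflict lies in 7d together with that omission; inclusion 2 is forward-looking and is not itself at fault.

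The conclusion rests on reading the criteria literally. Its size is 4% of the decision set per such patient. The effect on power or false-pass risk cannot be fixed from the documents, and the figures above depend on assumed counts and rates. It should be corrected because the repair is small and the affected patients cannot answer the trial's question.

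**What to change.** 1. Reconcile 7d with 5.5 and 5.5.3: remove the exemption for the resection craniotomy, or align it with the diagnostic biopsy that the protocol describes. 7d also names open biopsy, which 5.5.3 permits for diagnosis, so the two should be read together when the sentence is edited.
2. Add to 5.2.3 that prior resection or debulking of the current tumor is not allowed, consistent with the hypothesis in 4.1. If the sponsor does mean to admit such patients, the protocol has to say so and explain how they bear on the hypothesis.
3. Have the central review under inclusion 2 also confirm and record that only a biopsy has been done.
4. Add to 5.9 that, if any already-resected patient has been enrolled, the 17-of-25 result is reported with and without that patient. The result without them has fewer than 25 patients, so it is descriptive and does not carry the error rates of the stated rule.

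The cost is a few sentences in the next amendment and one extra item for central review. A few patients with an incomplete first resection become ineligible, which may slow accrual slightly.

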3. KPS>70
4. No contraindication for chemoradiation.
5. >18 years of age.
6. CBC/differential obtained within 28 days prior to registration, with adequate bone marrow function defined as follows:
 - a. Absolute neutrophil count (ANC) \geq 1,500 cells/mm³;
 - b. Platelets \geq 100,000 cells/mm³;
 - c. Hemoglobin \geq 8.0 g/dl (Note: the use of transfusion or other intervention to achieve Hgb \geq 8.0 g/dl is acceptable)
7. Adequate hepatic function within 28 days prior to registration, as defined below:
 - a. ALT and AST \leq 3 x ULN
 - b. Bilirubin \leq 1.5 ULN
8. Negative serum pregnancy test obtained for females of child-bearing potential within 28 days prior to step 2 registration.
9. Ability to get multiplanar contrast enhanced MRI

5.2.3 Exclusion Criteria

1. Recurrent, unresectable or multifocal malignant gliomas.
2. Any site of distant disease (for example, drop metastases from the GBM tumor site)
3. Prior radiation or chemotherapy or radiosensitizers for cancers of the brain and head and neck region; note that prior chemotherapy for a different cancer is allowable (except temozolomide).
4. Pregnancy or women of childbearing potential and men who are sexually active and not willing/able to use medically acceptable forms of contraception; this exclusion is necessary because the treatment involved in this study may be significantly teratogenic.
5. Patients treated on any other therapeutic clinical protocols within 30 days prior to registration.
6. Inability to undergo MRI (e.g., due to safety reasons, such as presence of a pacemaker, or severe claustrophobia).
7. Severe, active co-morbidity, defined as follows:
 - a. Transmural myocardial infarction within the last 6 months prior to registration
 - b. History of recent myocardial infarction 1month prior
 - c. New York Heart Association grade II or greater congestive heart failure requiring hospitalization within 3 months prior to registration.

- d. Serious or non-healing wound, ulcer or bone fracture or history of abdominal fistula, intra-abdominal abscess requiring major surgical procedure, open biopsy or significant traumatic injury within 28 days prior to registration, with the exception of the craniotomy for surgical resection
- e. Acute bacterial or fungal infection requiring intravenous antibiotics at the time of registration
- f. Hepatic insufficiency resulting in clinical jaundice and/or coagulation defects; note, however, that laboratory tests for coagulation parameters are not required for entry into this protocol.
- g. Chronic obstructive pulmonary disease exacerbation or other respiratory illness requiring hospitalization or precluding study therapy at the time of registration
- h. Acquired immune deficiency syndrome (AIDS) based upon current CDC definition; note, however, that HIV testing is not required for entry into this protocol. The need to exclude patients with AIDS from this protocol is because the treatments involved in this protocol may be significantly immunosuppressive with potentially fatal outcomes in patients already immunosuppressed.
- i. Any other severe immunocompromised condition.
- j. Active connective tissue disorders, such as lupus or scleroderma that in the opinion of the treating physician may put the patient at high risk for radiation toxicity.
- k. End-stage renal disease (i.e. on dialysis or dialysis has been recommended).
- l. Any other major medical illnesses or psychiatric treatments that in the investigator's opinion will prevent administration or completion of protocol therapy.

5.3 Recruitment

All patients seen by the Neuro-Oncology team in the Geisinger health system for fulfillment of the eligibility criteria will be invited to participate in the study. Nurse coordinators and clinical research staff would identify these patients for screening.

5.4 Study Duration

5.4.1 Approximate Duration of Subject Participation

The median progression-free survival for these patients is in the order of 8-12 months, and the median overall survival is in the order of 14-18 months. Subject participation will be from

registration to progression, death or 26 months after the enrollment of the last study participant. This includes registration, study treatment, postoperative phase, adjuvant therapy, and follow-up.

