5.4.2 Approximate Duration of Study

We estimate at least 15 patients a year will be enrolled in this study. With further follow-up of at least 26 months from registration to assess the progression free survival, this Phase II study would be completed in 3 years. The end of the study is the last visit of the last subject or end of collection of data from the patient's electronic health record or whichever is last.

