5.8 Secondary Endpoints

Overall survival.

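### Section 5.4.1, read naturally, ends follow-up at progression, although overall survival is the only secondary endpoint and no section provides for vital status after that

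*Combined protocol and SAP*

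**What the plan says.** Section 5.4.1 defines participation as running from "registration to progression, death or 26 months after the enrollment of the last study participant", and adds: "This includes registration, study treatment, postoperative phase, adjuvant therapy, and follow-up". It does not say whether the first or the last of these events applies. The same section puts median progression-free survival (PFS) at 8-12 months and states that "the median overall survival is in the order of 14-18 months".

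Section 5.8 reads, in full, "Overall survival". Specific Aim 2 (4.3) includes: "Assess the impact of improvements in local control on overall survival". The visible text gives OS no time origin and no censoring rule. Section 5.9.2 has primary and secondary endpoints evaluated once 25 patients are complete, with at least 7 months for the last patient treated.

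Section 5.4.2 states: "We estimate at least 15 patients a year will be enrolled in this study". It continues: "With further follow-up of at least 26 months from registration to assess the progression free survival". From these two inputs it concludes that "this Phase II study would be completed in 3 years". It ends the study at the later of the last visit and the end of health-record collection.

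**The concern.** OS needs the date of death, or the date last known alive, for every patient, whether or not the tumour has progressed. A participation rule that stops at progression removes that information from the patients most likely to die soon. Treating them as censored at progression breaks the independence of censoring that a Kaplan-Meier estimate relies on, and OS would look longer than it is.

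If staff look up deaths in the health record instead, the plan does not say for whom, how often or up to what date. Ascertainment could then differ between patients. This needs settling while patients are being followed, because survival contact that was missed may not be fully recoverable.

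**Working it through.** **1. What the participation rule means.** It names three end points: progression, death, and 26 months after the last enrolment. If the last of them governed, progression would never decide anything, because death cannot come before progression in a patient who progresses. Only a first-event reading gives that word a function. On the protocol's own medians, half the patients reach a PFS event by month 8-12, before the earliest possible 26-month limit, while half are still alive at month 14-18. Progression would therefore be the usual end of follow-up.

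**2. Whether another section supplies survival follow-up.**
- 5.4.2: health-record collection may outlast visits. This defines the end of the study, and names no survival purpose, schedule or cutoff.
- 5.5 and 5.5.7: salvage therapy is listed among the procedures and further therapy goes in the CRF. This is treatment data.
- 5.6: follow-up is 3-monthly after the 12-month timepoint, with no stop at progression and no vital-status row.
- 6.1 and 6.2: death is an SAE, and AEs and SAEs are recorded until withdrawal or death. It is not said whether leaving at progression counts as withdrawal.

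These sections point to data after progression. None provides for vital status.

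**3. Follow-up available at the 7-month floor.** Inputs: N = 25 and 7 months (5.9.2), and 15 patients a year (5.4.2). Assumption: uniform accrual at that stated minimum.
- Accrual: 25 / 15 × 12 = 20 months.
- Share with potential follow-up of at least t months = (floor month − t) / 20.

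Seven months counted from last enrolment: floor = 20 + 7 = month 27.
- t = 14: 13 / 20 = 65%.
- t = 18: 9 / 20 = 45%.

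Seven months counted from the last patient's surgery at week 12 (the late end in 5.6; treatment assumed to start at enrolment): 12 weeks = 2.8 months, so floor = 20 + 2.8 + 7 = month 29.8.
- t = 14: 15.8 / 20 = 79%.
- t = 18: 11.8 / 20 = 59%.

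Counted from completed adjuvant therapy, with six 28-day cycles after that surgery: 12 + 24 = 36 weeks = 8.3 months, and 8.3 + 7 = 15.3. Every patient could then have at least 14 months.

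At the 26-month limit in 5.4.1 (month 20 + 26 = 46), every patient could have 18 months under any of these readings.

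**4. Study duration (minor).** The stated figure is 3 years, or 36 months. Duration = N / 15 × 12 + 26.
- N = 25 (5.9.2): 20 + 26 = 46 months.
- N = 30 (5.2.1): 24 + 26 = 50 months.
- N = 24 (Abstract): 19.2 + 26 = 45.2 months.

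The stated figure is not reproduced for any of these. Finishing in 36 months leaves 36 − 26 = 10 months for accrual, which for N = 25 needs 25 / (10/12) = 30 patients a year.

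**The case against.** The strongest reply is that 5.4.1 is headed as approximate, states no first-event rule and quotes median OS just before the window. The sections listed in step 2 can be read as supplementing it, and the consent form, not among the visible pages, may describe survival follow-up. This stands in part: deaths after progression may well be captured in practice, and the conflict is less than certain. It does not remove the problem, because no visible section says that vital status is collected after progression.

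The consequence is also limited. OS is a secondary endpoint in a single-arm study with no OS hypothesis or decision rule. Kaplan-Meier estimation does not need every patient followed to the median, and the 7-month floor allows later reporting. All of that stands.

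A reader might go further in four ways that the documents do not support.
- *The 26-month windows contradict each other.* Those in 5.4.1 and 5.4.2 are compatible: 26 months after the last enrolment gives every patient at least 26 months from registration. Only footnote c in 5.6 differs, and no visible table row carries its marker.
- *OS has no data cutoff at all.* Two times are given, in 5.9.2 and 5.4.1. The fault is that they are not reconciled and that one is only a floor.
- *The gap between median PFS and median OS is the survival time that would be missed.* A difference of medians is not the median survival after progression.
- *Three years is impossible.* The accrual figure is a minimum, so 3 years is attainable at about twice that rate. The documents do not claim such a rate.

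**Conclusion.** The concern holds as a conflict between the participation rule in 5.4.1 and the only secondary endpoint. It rests on the first-event reading, which is the natural one but is not stated. Under it, OS is informatively censored at progression and biased upward, by an amount the documents cannot give. A reader might infer that deaths after progression will certainly be lost; the text shows only that nothing provides for collecting them.

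The shares at the 7-month floor (65% and 45%, or 79% and 59%) assume uniform accrual at 15 a year, and they depend on what the 7 months are counted from. The first pair is the low end. They show why the timing of final OS needs stating; they do not make an early estimate invalid.

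The duration discrepancy is administrative. The 7-month primary decision is unaffected by either point. A correction should be made, with moderate confidence.

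**What to change.** - **5.4.1:** state that progression does not end vital-status collection, which continues from the health record until death, withdrawal of consent or one stated data cutoff. The existing 26 months after last enrolment is one candidate; the choice is the sponsor's, since 5.4.2 ties its 26 months to PFS.
- **5.8 and 5.9:** define OS from a stated origin (registration, for example) to death from any cause, censored at the date last known alive and not at progression. Say whether OS is final at the 7-month report or at the later cutoff, and what the 7 months are counted from.
- **5.6 footnote c and 6.2:** reconcile with the above, without shortening AE or SAE recording.
- **5.4.2:** restate the duration from the reconciled sample size (about 46 months for 25 patients, 50 for 30, at 15 a year), or state the accrual rate that 3 years requires (about 30 a year for 25 patients).

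The cost is a wording amendment, periodic record checks, a consent sentence if the form does not already cover this, a longer stated duration and, if the later cutoff is chosen, a later final OS report. No visits or patients are added.
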